4.3. Secondary Endpoints

- 1. **AliveCor confirmed atrial fibrillation event** Daily self-reported atrial fibrillation event confirmed by report from AliveCor device.
- 2. Average frequency of AF episodes per week For each patient, the average number of AF episodes per week during the final month of each patient's enrollment as reported by the patient will be calculated.
- 3. Average duration of AF episodes per week For each patient, the average duration among all AF episodes per week during the final month of each patient's enrollment as reported by the patient will be calculated.
- 4. Average severity of AF episodes per week For each patient, the average severity among all AF episodes per week during the final month of each patient's enrollment as reported by the patient will be calculated.

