to continue to track their AF frequency and severity for 4 more weeks. During this 4 week period, participants will be able to implement any lifestyle changes they deem appropriate based on what they learned from their N of 1 trial. Following the completion of the 4 week "lifestyle change" period, participants will complete the AFEQT survey and will then have the option of either testing another AF trigger or concluding their study participation. Participants that choose to test additional triggers will have up to one week to start their next N-of-1 trial that will follow the same trigger testing protocol as the first. Participants will have the option of testing up to 5 triggers following this protocol.

Symptom Surveillance: Participants randomized to the symptom surveillance arm will engage in data tracking for a period of 10 weeks and receive daily reminders to complete study activities. Participants will be asked daily about the estimated total duration and severity of AF episode(s) and daily mood and sleep quality. They will also be asked to take AliveCor readings at least once per day and anytime they are experiencing AF symptoms. Participants will be able to visualize their AF data in real time and will receive a monthly summary of their AF frequency and severity via the Eureka app. At the end of the 10-week tracking period, participants will complete the AFEQT survey. Then, participants will have the option to cross over to engage in trigger testing. Participants that choose to test their triggers will be able to test up to 4 triggers, one trigger at a time, following the N-of-1 trial protocol described above.

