Meta-Analysis of N-of-1 Trials: The collection of individual N-of-1 trials can be thought of as a set of studies whose results can be combined as in a meta-analysis. The data can be considered as a multilevel structure in which a set of patients is studied with each patient having a set of measurements. Standard multilevel mixed model methods will be used to estimate the average effect and variance within and across patients. Across patient values estimate the average effect in the population of patients studied, while the within-patient estimates describe an improved estimate of each patient's true effect assuming exchangeability across patients. We will fit these models using a Bayesian multilevel model with non-informative priors in order to obtain posterior distributions of the within and between effect sizes. We will then compare the multilevel patient estimates with those from the patient's data alone in order to determine how much the effects change and how much additional precision these estimates gain.

Analysis of Comparative Effectiveness: The experimental design is a simple two-arm randomized trial comparing N-of-1 vs. symptom surveillance. The primary outcome is the change in the AFEQT scale from baseline to 12 weeks. The mean change in each treatment group will be compared by a t-test. The average frequency and severity of AF episodes per week during the final month of each participant's enrollment will be the secondary

outcomes. Their group means will also be compared with a t-test. We will check for balance in covariates across the randomized groups and will adjust for any imbalances by including those covariates in regression analyses and reporting the adjusted treatment effect as a secondary analysis.

Missing Data: A major purpose of this aim is to determine the feasibility and usability of N-of-1 studies for actual application in clinical practice. Therefore, carefully documenting adherence and completion rates and predictors of each will be an important aspect of this study. Within the HeH study, we have found that >90 % of all AF HeH study participants complete all AF-related surveys, including the AFEQT. The primary analysis will be intent-to-treat which uses all participants as randomized. When no endpoint is available, we will assume no change. Further analyses will employ multiple imputation to fill in missing values, particularly in covariate-adjusted models ([name]-3).

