N-of-1 Trial arm: Patients will use the Eureka mobile application and AliveCor device to execute at least one N-of-1 trial with the goal of identifying and better controlling their AF triggers. Each N-of-1 trial will last a total of 6 weeks and will include up to 3 periods of trigger exposure and 3 periods of trigger elimination with each exposure/elimination period lasting 1 week. Patients will be randomly assigned a sequence of trigger exposure and elimination periods such that they receive each treatment in each two-week block. During each N-of-1 trial, patients will track daily AF duration and severity, daily mood and sleep quality, daily AliveCor tracings and daily trigger exposure. At the end of each trial, patients will be able to review their trial results which will include visualizations of their daily AF symptom and trigger tracking over time. After completing a trial, patients will be instructed to implement any lifestyle changes they deem appropriate based on what they learned from the results of their trial. Patients will implement these changes for a period of 4 weeks during which they will continue to track AF episode duration and severity via the app. At the end of the 4-week lifestyle change period, patients will complete the Atrial Fibrillation Effect on Quality of Life survey (AFEQT) (Appendix A) and will then have the option of testing another trigger or ending their study participation.

Symptom Surveillance arm: Patients will use the Eureka app and AliveCor device to record daily AF duration and severity, daily AliveCor readings and daily mood and sleep quality for a period of 10 weeks. Patients will be able to visualize their AF, sleep and mood data in real time and will receive a weekly summary of their data via the Eureka app. At the end of the 10-week data tracking period, patients will complete the AFEQT survey and will then have the option of either ending their study participation or crossing over to the N-of-1 trial arm to test their triggers.

Primary Study Aim:

To test the comparative effectiveness of N-of-1 trials vs. data tracking alone to identify and eliminate individual level triggers and reduce AF frequency and severity as measured by the atrial fibrillation quality of life scale (AFEQT)

Secondary Aims:

- Using individual N-of-1 trials, identify modifiable exposures that increase the risk for an AF episode on an individual-level.

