5.4 Analysis

5.4.1 Comparison of N-of-1 to data tracking

The experimental design for Aim 2 is a two-arm randomized trial comparing N-of-1 vs. symptom surveillance. The primary endpoint is AF severity via the AFEQT from baseline to 10 weeks. Differences between treatment groups will be compared using analysis of covariance with the 10 week measurement as the outcome and the baseline measurement as covariate. We will also test for an interaction between treatment and baseline AFEQT in order to measure possible treatment effect heterogeneity. The average frequency, duration and severity of AF episodes per week during the final month of each patient's enrollment will be secondary outcomes. Their group means will be compared with a t-test. Additional secondary outcomes will include safety events: hospitalizations, emergency room visits, stroke, myocardial infarctions and heart failure. The main analysis will treat each of these as a binary outcome indicating the incidence of any event. We will also investigate models for multiple Version 1.0 5/12/17

events per person if these are common. We will check for balance in covariates across the randomized groups and will adjust for any imbalances by including those covariates in regression analyses and reporting the adjusted treatment effect as a secondary analysis. The null hypothesis of no difference will be tested at a significance level of 0.05.

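### The between-arm AF frequency, duration and severity outcomes lack a fixed time window, and duration and severity have no stated value for AF-free participants

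*SAP*

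**What the plan says.** SAP 4.3 defines frequency as "the average number of AF episodes per week during the final month of each" patient's enrollment. Duration and severity use the same month, each averaged over the AF episodes that occurred. SAP 5.4.1 makes "The average frequency, duration and severity of AF episodes per week during the final month of each" patient's enrollment the secondary outcomes and compares group means by t-test. Protocol 1.7.2 has "The average frequency and severity of AF episodes per week during the final month of each" participant's enrollment, without duration. The corresponding Table 2 rows also refer to the final month.

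Participation does not have to stop at week 10. After the 10-week AFEQT, controls choose between "ending their study participation or crossing over to the N-of-1 trial arm to test their triggers" (SAP 2). For controls who cross over, Protocol 1.5 says: "Participants that choose to test their triggers will be able to test up to 4 triggers". For the N-of-1 arm it says: "Participants will have the option of testing up to 5 triggers following this protocol". Up to a week may pass before each further trial.

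On scoring, SAP 4.2 gives an AF-free day a duration of 0 and a severity of 1. SAP 5.4.1.2 treats days with no reported event as event-free and concludes that these outcomes will have no missing values. In Table 2, 0 means no answer in the duration and severity rows, and the monthly frequency count is given a range of 0-7.

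**The concern.** Two features of the definitions can spoil a randomized comparison.

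- **Time.** If enrollment lasts as long as a participant stays, the scored month is set by later choices: crossing over, testing more triggers or leaving early. Arms and individuals are then measured at different times, and some controls after they have received the intervention.
- **Selection.** An average over AF episodes exists only for people who had AF in the window. Having AF is itself an outcome, so the t-tests for duration and severity would compare subsets formed after randomization.

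The trial's stated objective is to reduce AF frequency and severity, and these outcomes measure that directly between arms. As written, two competent analysts could defend different datasets and different scores.

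**Working it through.** The plan gives no figure to reproduce here. The check is schedule arithmetic plus illustrations under assumed rates.

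**Where the final month falls.** Each trigger takes 6 testing weeks + 4 lifestyle-change weeks = 10 weeks (Protocol 1.4.1, SAP 2). The gap between trials is 0 to 1 week (Protocol 1.5). I assume the same gap before a crossed-over control's first trial.

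- N-of-1 with k triggers ends at week 10k to 10k + (k - 1).
- A control crossing over for k triggers ends at week 10 + 10k to 10 + 11k.

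| Participant | Last week | Final four weeks |
|---|---|---|
| N-of-1, leaves after week 6 | 6 | 3-6 |
| N-of-1, 1 trigger | 10 | 7-10 |
| N-of-1, 2 triggers | 20-21 | 17-20 or 18-21 |
| N-of-1, 5 triggers | 50-54 | from 47-50 to 51-54 |
| Control, stops | 10 | 7-10 |
| Control, crosses over, 1 trigger | 20-21 | 17-20 or 18-21 |
| Control, crosses over, 4 triggers | 50-54 | from 47-50 to 51-54 |

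SAP 2 randomizes the sequence so that "they receive each treatment in each two-week block". Weeks 3-6 are therefore two exposure and two elimination weeks.

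**Possible size of the window effect (assumed rates).** Let a share c of controls cross over and gain the full effect, and a share n of N-of-1 participants test more triggers and gain an extra fraction g. The literal-window difference is then (1 + n×g - c) times the week 7-10 effect.

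- c = 0.50, g = 0: 1 + 0 - 0.50 = 0.50.
- c = 0.10, n = 0.50, g = 0.50: 1 + 0.25 - 0.10 = 1.15.

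The range spans 1, so the direction is not fixed.

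**Scoring one participant.** Take 28 days with 2 AF days, one 120-minute episode on each, severity 5.

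- Duration: 120 minutes per episode (4.3), or 2×120/4 = 60 minutes per week as total burden.
- Severity: 5 among episodes (4.3), or (2×5 + 26×1)/28 = 1.29 with the 4.2 daily values.
- With no AF days, both 4.3 averages are 0/0. The 4.2 values would be 0 and 1, and severity 1 is also the mildest AF grade.

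**How many would have no 4.3 value (assumed Poisson).** The AF-free share over the window is exp(-rate). At 1, 2 and 4 episodes per four weeks it is 37%, 14% and 2%, or about 88, 32 and 4 of 239 per arm. The documents give no AF rate. The preamble to the Appendix E trigger survey mentions at least one episode a month, but that is not an inclusion criterion.

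**Selection.** Suppose half the participants have one 1-hour episode and half one 10-hour episode. The control mean is 0.5×1 + 0.5×10 = 5.5 h.

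- AF cleared in 30% of the 1-hour half: (0.35×1 + 0.5×10)/0.85 = 6.29 h, 14% worse. Total AF time is 5.35/5.5, a fall of 3%.
- AF cleared in 30% of the 10-hour half: (0.5×1 + 0.35×10)/0.85 = 4.71 h, 14% better. Total AF time is 4.0/5.5, a fall of 27%.

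AF days fall 15% in both cases, yet the 4.3 mean moves in opposite directions.

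**Severity.** With grade 4 in both arms and 25% versus 15% AF-free, the means are 4.0 versus 4.0 if AF-free participants are dropped. If they are scored 1, the means are 4×0.75 + 0.25 = 3.25 versus 4×0.85 + 0.15 = 3.55.

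**Dropout once the window is fixed.** If 20% of the N-of-1 arm and 10% of controls leave before week 7 (assumed), with no true effect, counting their later days as event-free gives 1 - 0.80/0.90 = an 11% apparent reduction in AF frequency.

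**The case against.** The best reply is that weeks 7-10 are obvious. The SAP summary speaks of a 10-week study period, the N-of-1 schedule is 6 + 4 weeks so its last month is the lifestyle-change period, and Table 2 schedules the safety items at 4 and 8 weeks. The AliveCor row of Table 2 also breaks off, in the text available, in what looks like a between-arm window statement. I accept that this was the likely intent. But the written rule refers to each individual's enrollment, Protocol 1.7.1 also speaks of a 6-month study, and nothing legible excludes later data.

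A second reply is that SAP 4.2 already supplies values for AF-free days and 5.4.1.2 makes unreported days event-free. That is so: the gap is which rule governs the between-arm analysis, because 4.3 does not adopt those values.

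A reader might infer that Table 2 sets up a rival monthly total for duration. Its range of 0-60 minutes and 0-24 hours, with daily timing, reads better as one day's entry. The real mismatch is the code 0, which means no answer there and no event in 4.2. Likewise, the 0-7 frequency range fits AF days per week, and SAP 5.4.2 already treats frequency in the individual trials as yes or no per day. Both rows need aligning, but neither shows a competing endpoint.

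**Conclusion.** The point holds and should be fixed before arm-level data are seen. The window is not fixed in any legible text, and the literal reading can place the scored month as early as weeks 3-6 for someone who leaves after week 6 and as late as weeks 51-54. The 4.3 duration and severity averages have no value for AF-free participants, contradict the no-missing-values statement, and condition on an event after randomization.

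Three stronger readings are not supported.

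- That the plan necessarily dilutes the effect or makes the intervention look harmful: bias can go either way, and every rate-based figure above is an illustration under assumed rates.
- That the primary analysis is compromised: the SAP's AFEQT comparison is fixed at 10 weeks and is unaffected.
- That the Protocol's primary is measured after crossover because "The primary outcome is the change in the AFEQT scale from baseline to 12 weeks". Devices ship over two weeks after randomization (Protocol 1.5), so 12 weeks from randomization may equal 2 + 10 weeks of tracking. Counted from the start of tracking, it would fall after crossover opens. The clock origin is not stated, so the discrepancy needs reconciling, but no more can be concluded.

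**What to change.** - **Window.** In SAP 4.3, 5.4.1, Table 2 and Protocol 1.7.2, define it as weeks 7-10 after the start of tracking in both arms, and exclude later data from the between-arm comparison. Anchor on tracking: with two weeks of shipping, weeks 7-10 from randomization would be about tracking weeks 5-8, two of them inside trigger testing.
- **Scoring.** Analyse AF days per week and total AF minutes per week, with 0 on AF-free days. Report severity among AF days descriptively.
- **Table 2.** Align it with 4.3, including the no-answer code of 0 and the 0-7 range.
- **Missing data.** Amend 5.4.1.2 so that days after withdrawal are missing, handled for example by multiple imputation, with the event-free assumption kept as a sensitivity analysis. Say how withdrawal is recognised, since silence in an app study can look the same.
- **Separately.** State the clock origin and reconcile the Protocol's 12-week AFEQT time point with the SAP's 10 weeks.

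The cost is wording and a small imputation step. Daily AF yes/no, total duration and severity are already collected, and the sample size does not change. Weekly totals will be skewed, so the planned t-test fits them less comfortably.

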4.4. Safety Endpoints

- 1. **Hospitalization** Days on which any hospitalization occurs together with date and hospital location. This will be recorded from the Eureka app and will be reported monthly by the patient.
- 2. **Hospitalization related to atrial fibrillation** Days on which a hospitalization related to atrial fibrillation occurs together with date and hospital location. This will be recorded from the Eureka app and will be reported monthly by the patient.
- 3. **Emergency department visit** Days on which any emergency department visit occurs together with date and hospital location. This will be recorded from the Eureka app and will be reported monthly by the patient.
- 4. **Cerebrovascular accident** Days on which any cerebrovascular accident occurs together with date and hospital location. This will be recorded from the Eureka app and will be reported monthly by the patient.
- 5. **Myocardial infarction** Days on which a myocardial infarction occurs together with date and hospital location. This will be recorded from the Eureka app and will be reported monthly by the patient.
- 6. **Heart failure** Days on which heart failure occurs together with date and hospital location. This will be recorded from the Eureka app and will be reported monthly by the patient using language from previous HeH surveys.

4.5 Potential Treatment Effect Modifiers

Within the N-of-1 experiments and in the comparison of N-of-1 to data tracking, it is recognized that external factors could influence willingness to adhere to a treatment assignment, could interact with the exposure and AF, and could affect AF episodes. Per suggestions from AF patients, we will therefore perform daily assessments of mood, sleep (the night previous) and stress. These will be obtained via push notifications and will therefore rely on patient self-report. Relationships between these factors and both treatments (N-of-1 and usual care) and outcomes will be investigated; given evidence of statistically significant relationships, results will be adjusted for these covariates.

1. **Medical History:** Characteristics as outlined in Table 2 collected at baseline by self-report include hypertension, diabetes, heart failure, history of cerebrovascular accident, first degree Version 1.0 5/12/17

family member with atrial fibrillation and history of atrial fibrillation and history of no disease other than atrial fibrillation.

- 2. **Demographics:** Basic demographic data as outlined in Table 2 including age, gender, race/ethnicity, height, weight, and education level will be collected both to describe the population of patients and to assess for heterogeneity of treatment effects at the population level.
- 3. **Current medications:** Current medications being taken including antiarrhythmic drugs, aspirin, Plavix, warfarin or others as noted in Table 2 will be recorded.
- 4. **Mood and sleep:** Patient self-report on mood and sleep will be collected via short survey on the Eureka app on a daily basis.

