1.4 Study Design

This is a randomized controlled trial that examines the comparative effectiveness of N-of-1 study protocols vs. symptom surveillance (data tracking alone) for reducing AF episode frequency and severity (Figure 1). Throughout the duration of the study, all study participants will use the Eureka mobile app to self-report daily mood and sleep quality, AF episode duration (in minutes) and severity, and will use the AliveCor mobile electrocardiogram (ECG) to record ECG tracings. Participants will be instructed to take ECG tracings at least once per day as well as any time they think they are having an AF episode. Participants will be able to visualize their data in real time and will receive weekly summaries of their AF frequency and severity via Eureka. Due to the rapid growth and availability of mobile apps and devices that can monitor AF episodes, we believe the symptom surveillance condition is a realistic and appropriate comparison group.

[figure not shown]

Figure 1: Study Design

In addition to tracking mood, sleep and AF data, participants in the N-of-1 trial arm of the study will also test their triggers and track their trigger exposure. N-of-1 trials will be conducted using a

citizen health-scientist approach where patients are empowered and supported in independent experimentation. Together with the HeH Alliance Patient Advisory Board (PAB), the study team designed a menu of triggers that participants will select from to test in their personal AF triggers in a rigorous testing environment. These N-of-1 trials will consist of 6 randomly assigned periods of exposure (trigger exposure/trigger "on") and elimination (avoiding trigger/trigger "off").

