1.5 Study Procedures

Randomization/Baseline evaluation: Potential participants will be identified via the Health eHeart Study and the StopAfib.org patient advocacy organization and reached out to via email campaigns. Of note, invitations will be extended broadly to include friends family and acquaintances of those participants. Patients may also be recruited directly from UCSF clinics or other web-based sources of potentially interested atrial fibrillation patients. The study email campaign will contain an overview of the study. If the patient is interested in participating in the study there will be a link for the participant that will take them to the mobile app store to

download the Eureka app. Potential participants will be prompted to register an account and will complete an inclusion/ exclusion criteria survey within the Eureka app. If eligible, they will continue on to the study consent form (Appendix B). Upon completion of the electronic study consent, Eureka will randomize participants to either the N-of-1 or the symptom surveillance arm of the study with a 1:1 allocation ratio.

Participants will then be asked to complete baseline data collection which will include basic demographics, medical history, and current atrial fibrillation medications. After baseline data collection, the study team will ship AliveCor devices to study participants over a period of two weeks. At the end of this two week period, participant will be prompted to visit the Eureka application to complete a device consent and then will be instructed to download the AliveCor app and link their AliveCor device to their Eureka account. All participants will then complete the Atrial Fibrillation Effect on QualiTy of Life survey (AFEQT) (Appendix A). Once they complete the survey, the app will show participants which study arm they have been randomized to and prompt them to begin the appropriate study activities.

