5.1 Overview

Figure 2 details the study design for Aim 2 which is designed as an RCT to compare use of N-of-1 studies vs. symptom surveillance (data tracking alone) using comparable mHealth technology in both study arms. Working with the HeH patient stakeholders, we will design a menu of triggers that people with AF may select to test in their own personal N-of-1 study. This menu will include approaches for modifying triggers including alcohol, caffeine, exercise (frequency and intensity), sleep, liquid intake/dehydration,

meal size, sleep position (e.g., lying on left side), beverage and food temperature, or choices at the option of the patient. These N-of-1 protocols will involve 6 randomly assigned treatment periods (each 1-week in duration) of exposure (trigger "on") and elimination (trigger "off").

Figure 2

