5.3 Randomization to Treatments

Completion of the electronic consent via the Eureka portal will trigger 1:1 randomization to the N-of-1 or the symptom surveillance conditions. The randomization schema will be conducted within the Eureka platform and communicated directly to patients via the mobile app.

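### SAP 4.5 adjusts the arm comparison for daily mood, sleep and stress recorded after randomization when significance tests are met, and does not rank that result against the 5.4.1 ANCOVA

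*SAP*

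**What the plan says.** SAP 4.5 opens with its scope: "Within the N-of-1 experiments and in the comparison of N-of-1 to data tracking". It plans daily assessments of mood, sleep and stress and then states: "Relationships between these factors and both treatments (N-of-1 and usual care) and outcomes will be investigated". What follows from that investigation is a commitment, not an option: "given evidence of statistically significant relationships, results will be adjusted for these covariates". It gives no test, threshold, summary measure or analysis rank.

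On timing:

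- SAP 5.3: "Completion of the electronic consent via the Eureka portal will trigger 1:1 randomization".
- Protocol 1.5: after the baseline AFEQT, "the app will show participants which study arm they have been randomized to and prompt them to begin the appropriate study activities". The baseline collection described there covers demographics, medical history and AF medications, not mood or sleep.
- Protocol 1.4: "Throughout the duration of the study, all study participants will use the Eureka mobile app to self-report daily mood and sleep quality". SAP Table 2 times both as daily, with no baseline value, and 4.5 repeats this: "Patient self-report on mood and sleep will be collected via short survey on the Eureka app on a daily basis".
- SAP 5.1, on what participants may test: "This menu will include approaches for modifying triggers including alcohol, caffeine, exercise (frequency and intensity), sleep".

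On analysis, SAP 5.4.1 specifies an ANCOVA of the 10-week AFEQT with baseline AFEQT as covariate. It adds an analysis adjusted for covariates found imbalanced between arms, reported as secondary; Protocol 1.7.2 has the same secondary analysis. SAP 5.4.1.1 makes treatment interactions with mood and sleep exploratory. None of these sections refers to the adjustment rule in 4.5.

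**The concern.** Mood, sleep and stress are measured after assignment, in people who know their arm, and sleep can itself be the behaviour being tested. A difference between arms in such a measure arises either by chance or because the intervention caused it. A rule that fires when the measure is significantly related to arm fires mostly in the second case. There, holding the measure fixed removes part of a real effect. It can also create an apparent effect where none exists, if the measure and AFEQT share other causes.

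Because 4.5 gives the adjusted result no place in the hierarchy, it could be reported beside the 5.4.1 result, or in place of it, once the data are known. The summary of 70 daily entries, the test and the threshold would also be chosen at that stage. Mood is recorded as six unordered categories. Stress has no item of its own in Table 2, only a Stressed category of mood.

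**Working it through.** **Inputs from the documents.** 239 per arm, SD 19 and a 5-point difference (SAP 5.2); significance level 0.05 (SAP 5.4.1), taken as two-sided.

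**Assumptions, not in the documents.** The correlation of baseline with 10-week AFEQT is 0.5. M is a single mood/sleep summary with SD 1. Its correlation with 10-week AFEQT, a, is 0.2 or 0.4. Its correlation with baseline AFEQT, b, is 0, a/2 or a. The arm shifts M by d = 0 to 0.3 SD. The rule is read as: adjust only if M is significant at 0.05 for both arm and AFEQT.

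**1. The plan's own figure.** n = 2(1.960 + 0.842)² × 19² / 5² = 226.7, so 227 per arm for 80% power. At 239 per arm power is 82%. The stated 80% is met, and nothing below depends on the gap.

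**2. The 5.4.1 ANCOVA.** Residual SD = 19 × √(1 − 0.5²) = 16.45. SE = 16.45 × √(2/239) = 1.505. For 5 points, z = 3.32, and power = Φ(3.32 − 1.96) = 91%. In the simulations below with no true effect, its bias was 0.0 and its type I error 4.4% to 5.6%.

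**3. Bias if M is always added.** The slope of AFEQT on M given baseline is g = 19 × (a − 0.5b)/(1 − b²), and the arm estimate moves by −g × d. At d = 0.3:

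- a = 0.4, b = 0: 19 × 0.4 × 0.3 = 2.28 points
- a = 0.4, b = 0.2: 19 × 0.3125 × 0.3 = 1.78 points
- a = 0.4, b = 0.4: 19 × 0.2381 × 0.3 = 1.36 points
- a = 0.2, b = 0.2: 19 × 0.1042 × 0.3 = 0.59 points

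**4. How often the arm test fires.** Approximately Φ(d/√(2/239) − 1.96), plus the opposite tail where d is small: 5% at d = 0, 19% at 0.1, 59% at 0.2 and 91% at 0.3. The larger the effect on M, the more often the rule applies.

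**5. The full rule, no true effect on AFEQT.** Simulation, 8,000 replicates per scenario. Cells give bias in points (type I error); the last three columns are b = 0, b = a/2 and b = a.

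| d | a | b = 0 | b = a/2 | b = a |
|---|---|---|---|---|
| 0.2 | 0.2 | −0.56 (6.5%) | −0.46 (5.9%) | −0.31 (5.8%) |
| 0.2 | 0.4 | −1.13 (13.5%) | −0.89 (9.6%) | −0.69 (8.1%) |
| 0.3 | 0.2 | −1.09 (11.2%) | −0.81 (8.7%) | −0.57 (6.8%) |
| 0.3 | 0.4 | −2.18 (36.6%) | −1.69 (21.5%) | −1.31 (14.7%) |

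At d = 0 the bias is between −0.02 and +0.01, with error 4.4% to 5.0%. At d = 0.1 it is −0.09 to −0.35, with error 4.5% to 5.3%. The d = 0.3 rows sit just inside the closed-form values in step 3, as they should when the rule fires about nine times in ten.

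**6. The full rule, true effect 5 points.** Cells give the mean estimate (power), against 5.0 (91%) for ANCOVA.

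| d | a | b = 0 | b = a/2 | b = a |
|---|---|---|---|---|
| 0.2 | 0.2 | 4.40 (84.0%) | 4.57 (86.6%) | 4.70 (88.0%) |
| 0.2 | 0.4 | 3.83 (77.5%) | 4.09 (80.1%) | 4.31 (82.0%) |
| 0.3 | 0.2 | 3.93 (75.4%) | 4.20 (79.0%) | 4.42 (83.5%) |
| 0.3 | 0.4 | 2.86 (54.7%) | 3.30 (62.3%) | 3.74 (70.5%) |

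**7. Sensitivity.** If one significant link is enough to trigger adjustment, the d = 0.2 to 0.3 null range becomes −0.40 (6.0%) to −2.28 (39.5%). Sleep was also modelled as collected: five levels, the mean of 70 daily entries, and an assumed 0.3 of daily variance between persons. With no effect, d = 0.3 and a = 0.4, that gives −2.05 (33.9%), −1.63 (21.1%) and −1.17 (12.0%) across the three values of b. The signs assume that the arm improves mood or sleep; they reverse if it worsens them.

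**The case against.** **The rank can be inferred.** A significant relationship between a covariate and arm is an imbalance. SAP 5.4.1 and Protocol 1.7.2 adjust for imbalances as a secondary analysis and do not restrict that to baseline covariates. SAP 4.5 also sits under data considerations, and where section 5 takes up mood and sleep for the arm comparison it makes them exploratory. This has some force: 4.5 does not say that its result replaces the ANCOVA. But the rank is at most inferable. The 5.4.1 rule has its own trigger and no link to 4.5, and the exploratory label covers interactions only. Even under this reading, a possible effect of the intervention would be adjusted away as if it were an imbalance.

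**The large figures rest on assumed shifts.** This stands. The only mechanism the documents name is sleep on the trigger menu. If one participant in eight chose it (an assumption) and changed by 0.8 SD, the arm-wide shift is 0.8/8 = 0.1 SD. If the change covered only the elimination and lifestyle weeks, it is 0.1 × 7/10 = 0.07 SD. At that size the bias is negligible.

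**The 37% is a corner case.** Also true. It needs M to correlate 0.4 with 10-week AFEQT and not at all with baseline; with equal correlations the figure is 15%. The unstated test matters too. If the AFEQT link is tested inside the ANCOVA, then at d = 0.3 and equal correlations of 0.2 the rule fires in about 64% of trials, with −0.41 points and 5.3% error.

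**One summary score is not how mood is recorded.** Correct: mood is nominal, and only sleep was checked as collected.

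**Conclusion.** The concern holds. SAP 4.5 commits the between-arm results to a significance-triggered adjustment for variables measured after randomization, and does not say how that result ranks against the 5.4.1 ANCOVA. The ANCOVA itself is sound and unchanged.

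The direction is general: if the arm shifts mood or sleep and these are related to AFEQT given baseline, the adjusted estimate is biased for the total effect of assignment. The size is conditional on the assumptions listed with the calculation. It is nil with no shift and trivial at 0.1 SD. At 0.2 to 0.3 SD with no true effect, it is 0.3 to 2.2 points with type I error from 6% to 37%. With a true 5-point effect, the estimate is 4.7 to 3.8 points (power 88% to 78%) at 0.2 SD and 4.4 to 2.9 points (84% to 55%) at 0.3 SD. The documents do not say which shift to expect.

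This conclusion does not extend to the individual N-of-1 analyses, whose methods SAP 5.4.2 refers to Aim 1 and which are not set out in these documents.

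**What to change.** In SAP 4.5, delete the significance-triggered adjustment for between-arm results. State there, with a cross-reference in 5.4.1, that:

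- the 5.4.1 ANCOVA is the primary result;
- no primary or secondary between-arm estimate is adjusted for mood, sleep or stress recorded after randomization;
- the imbalance-adjusted secondary analysis in SAP 5.4.1 and Protocol 1.7.2 stays, limited to baseline covariates, and the secondary t-tests stay as they are;
- any between-arm analysis using daily mood, sleep or stress, for example a mediation analysis, is exploratory and never replaces the primary.

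Also say whether stress is a separate daily item or the Stressed category of mood. That is a clarification and not part of the bias argument.

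The cost is SAP wording only. No analysis in 5.4.1 is removed and no new data are needed.
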